### Cycle 1 Day 1: Initiation of nivolumab plus ipilimumab

At each study visit, performance status, vital signs (including oxygen saturation), a physical exam, toxicity evaluation, review of current medications and blood tests will be performed. Blood tests must be performed on the day of the study visit.

Nivolumab 3mg/kg IV and ipilimumab 1mg/kg will be initiated on cycle 1, day 1.

Cycle 2 Day 1 (+/- 3 days) – Treatment visit, blood collection, toxicity visit

At each drug-administration visit, performance status, vital signs (including oxygen saturation), a physical exam, toxicity evaluation, review of current medications and blood tests will be performed. Blood tests must be performed on the day of the study visit or within the 2 days prior to the study visit.

Patient will be treated with Nivolumab 3mg/kg IV alone on Cycle 2 Day 1.

Cycle 2 Day 8 (should be same day as C2D8 biopsy, +/- 1 day from date of biopsy) – Research blood collection

Patients will have research blood collection on C2D8.

Cycle 2 Day 8 (+/- 1 week) – On-treatment tumor biopsy

An on-treatment tumor biopsy of (ideally) a non-target lesion will occur on C2D8 (+/- 1 week, i.e. during week 3-4 of study treatment). Acceptable samples include core needle biopsies for tumor tissue or lymph nodes or excisional, incisional, punch, or forceps biopsies for cutaneous or subcutaneous lesions. The safest and most feasible tissue biopsy is preferred and will be at the discretion of the treating physician. For core needle biopsies, five cores are preferred but at least three cores should be obtained; 1 will be fixed in formalin, 3 will be immediately frozen and then stored, and 1 will be processed fresh to isolate CD4/CD8+ cells prior to freezing.

Cycle 3 Day 1 (+/- 3 days) – Treatment visit, toxicity visit

At each drug-administration visit, performance status, vital signs (including oxygen saturation), a physical exam, toxicity evaluation, review of current medications and safety blood tests will be performed. Blood tests must be performed on the day of the study visit or within the 2 days prior to the study visit. Research bloods will be collected at C3D1 visit.

Patient will be treated with Nivolumab 3mg/kg alone on C3D1.

Cycle 4 Day 1 (+/- 3 days) – Treatment visit, toxicity visit

At each drug-administration visit, performance status, vital signs (including oxygen saturation), a physical exam, toxicity evaluation, review of current medications and safety blood tests will be performed. Blood tests must be performed on the day of the study visit or within the 2 days prior to the study visit. Research bloods will be collected at C4D1 visit.

Patient will be treated with both Nivolumab 3mg/kg and Ipilimumab 1mg/kg on C4D1.

#### Subsequent study visits

Patients will return for nivolumab administration, blood collection, and toxicity visit every two weeks (+/- 3 days) thereafter. Patient will be treated with both nivolumab and ipilimumab on Day 1 of every third cycle (i.e. every six weeks, +/- 3 days). Performance status, vital signs (including oxygen saturation), a physical exam, toxicity evaluation, review of current medications, and blood tests will be performed at each visit. Research bloods will be collected at C5D1 and at end-of-treatment visit. Blood tests must be performed on the day of the study visit or within the 2 days prior to the study visit.

#### Tumor assessment with CT scan – Beginning Week 6 (+/- 1 week)

Tumor assessments must include at least CT scans of the chest (+/- abdomen/pelvis depending on sites of known disease). IV (and PO, if abdomen/pelvic CT obtained) contrast is preferred but not required. Bone or PET scans are not adequate for assessment of RECIST 1.1 response in target lesions. The same radiographic procedure should be used to assess disease sites at screening should be used throughout the study (e.g. the same contrast protocol for CT scans). All known sites of disease must be documented at screening and re-assessed at each subsequent tumor evaluation (with exception of CNS lesions which do not need to be examined at each assessment). Scans should be performed and response assessed by RECIST v1.1 prior to patient's next study visit to determine if treatment should be continued.

Tumor assessments will be performed after 6 weeks (+/- 1 week) and subsequently every six weeks (+/- 1 week) while on study until week 48. After week 48, tumor assessments will be conducted every 12 weeks (+/- 1 week). Additional tumor assessments may be performed at the discretion of the treating physician.

#### Toxicity monitoring and adverse events

Patients should be assessed for toxicity at least every 2 weeks so long as patient remains on study. Safety blood tests must be performed on the day of the study visit or within the 2 days *prior* to the study visit.

Toxicity will be evaluated in this study through the monitoring of all serious and non-serious AEs, defined and graded according to NCI CTCAE v4.0.

#### Follow-up Assessments Prior to Progression of Disease

Patients who discontinue study treatment early for reasons other than disease progression (e.g. toxicity) should continue to undergo scheduled tumor assessments per protocol until the patient experiences confirmed progression, starts new anti-cancer treatment, withdraws consent, or dies, whichever occurs first.

#### Treatment beyond Disease Progression:

Accumulating evidence indicates a minority of subjects treated with immunotherapy may derive clinical benefit despite initial evidence of PD (115). Subjects treated with nivolumab plus ipilimumab will be permitted to continue nivolumab plus ipilimumab treatment beyond initial RECIST 1.1 defined PD, assessed by the investigator, as long as they meet the following criteria:

- Investigator-assessed clinical benefit, and do not have rapid disease progression.
- Tolerance of study drug
- Stable performance status
- Treatment beyond progression will not delay an imminent intervention to prevent serious complications of disease progression (e.g., CNS metastases)
- Subject provides written informed consent prior to receiving additional nivolumab treatment acknowledging the possibility of any reasonably foreseeable risks or discomforts, as well as the possibility of alternative treatment options.

The assessment of clinical benefit should take into account whether the subject is clinically deteriorating and unlikely to receive further benefit from continued treatment.

If the investigator feels that the nivolumab plus ipilimumab subject continues to achieve clinical benefit by continuing treatment, the subject should remain on the trial and continue to receive monitoring according to the Study Calendar in Section 10.0. A radiographic assessment/CT scan should be performed no earlier than 4 weeks after original PD to determine whether there has been a decrease in the tumor size or continued PD.

For the subjects who continue nivolumab plus ipilimumab study therapy beyond progression, further progression is defined as an additional 10% increase in tumor burden compared to baseline above the degree of progression determined at the time of initial PD (e.g. if progression of disease is determined with 24% growth from baseline and a subsequent confirmatory scan shows 33% growth compared to baseline (but 9% growth compared to initial PD) patient can continue on therapy. However, if there is 36% growth compared to baseline (and 12% growth compared to initial PD, patient should be discontinued from study treatment). This includes an increase in the sum of diameters of all target lesions and/or the development of new measurable lesions.

New lesions are considered measurable at the time of initial progression if the longest diameter is at least 10 mm (except for pathological lymph nodes which must have a short axis of at least 15 mm). Any new lesion considered non-measurable at the time of initial progression may become measurable and therefore included in the tumor burden volume if the longest diameter increases to at least 10 mm (except for pathological lymph nodes which must have a short axis of at least 15 mm).

Nivolumab/ipilimumab treatment should be discontinued permanently upon documentation of further progression.

#### Palliative Local Therapy

Palliative local therapy, including palliative (limited-field) radiation therapy and palliative surgical resection, is permitted prior to discontinuation of study treatment if the following criteria are met:

- 1) The subject is considered to have clinically or radiographically progressed at the time of palliative local therapy and meets criteria to continue with treatment beyond progression in the section above.
- 2) The lesion planned for palliative local radiation is not a target lesion used for assessing radiographic response
- 3) The case is discussed with the PI-Sponsor prior to the initiation of palliative local therapy. Palliative therapy must be clearly documented as such in the study record.

The potential for overlapping toxicities with radiotherapy and nivolumab plus ipilimumab currently is not known. If palliative radiotherapy is required for a tumor lesion, study therapy should be withheld for at least 1 week before, during, and 1 week after radiation. Subjects should be closely monitored for any potential toxicity during and after receiving radiotherapy, and AEs should resolve to Grade ≤ 1 prior to resuming nivolumab or ipilimumab.

Follow-up Assessments after Last Dose of Study Treatment

Patients will be followed for safety for 100 days following their last dose of study treatment. Patients who have an ongoing study-treatment related adverse event at the time of study completion or at discontinuation from the study will be followed until one of the following occurs: the event has resolved to baseline grade, the event is assessed by the study doctor as stable, new anti-cancer treatment is initiated, the patient is lost to follow-up, the patient withdraws consent, or it has been determined that the study treatment or participation was not the cause of the AE.

All patients will be followed for survival and subsequent anti-cancer therapy approximately every 3 months until death, loss to follow-up, or study termination.

End of Study

The end of study is defined as the date of the last follow-up visit of the last patient enrolled and is expected to occur approximately 4 months after the last patient enters the study.

**10.0 EVALUATION DURING TREATMENT/INTERVENTION**

	Screening	C1D1	C2D1	C2D8	C3D1	Each cycle thereafter Day 1	Final visit 
	Within 28 days of C1D1 unless otherwise noted		+/- 3 days	See note below 	+/- 3 days	+/- 3 days	100 days after last dose of study therapy (+/- 2 weeks)
Informed screening consent 	X						
Informed treatment consent	X						
History  , Physical 	X	X	X		X	X	X

Pregnancy test for WOCBP 	X 						
Comprehensive metabolic panel, Mg, LDH, amylase, lipase 	X	X	X		X	X	X
Complete blood count 	X	X	X		X	X	X
Thyroid function test 	X	X				Every third cycle	X
Hepatitis B, C, HIV	X						
EKG	X						
Adverse event assessment and attribution 	X	X	X		X	X	X
Radiographic tumor assessment 	X					Every 6 (or 12) weeks 	X
Research blood tests	X 	X 	X 	X 	X 	C4D1, C5D1 	X 
Pre-treatment tumor resection or biopsy	X (resection permitted within 12 weeks)						
Biopsy				X 			
Nivolumab 3mg/kg q 2 weeks		X	X		X	X	
Ipilimumab 1 mg/kg q 6 weeks		C1D1 and every 6 weeks (+/- 3 days)					

 Patients will be consented separately for screening consent by either medical oncologist or thoracic surgeon.

 Medical history includes baseline symptoms as well as detailed history of prior cancer therapies including start and stop dates, disease progression during or after therapy, as well as discontinuations due to intolerability or any other serious illness

 Body height to be measured at screening only

 Vital signs include weight, temperature, pulse, blood pressure, and oxygen saturation

 Full physical exam for baseline and end of study visit. Other study visit physical exams may be symptom directed.

 Applicable for women of childbearing potential. Serum or urine beta-HCG test within 3 days before the first dose of study drug.

 Screening safety blood tests (CBC and CMP) must be done within 28 days of C1D1. Subsequent safety blood tests may be performed the day of the study visit or within 2 days *prior* to the study visit.

 Thyroid function tests (TSH, reflexive free T4/free T3 if TSH is abnormal) should be performed at baseline, C4D1, and then D1 of every third cycle thereafter.

 Adverse events will be graded and attributed using CTCAE 4.0

 Tumor assessments will be performed with CT scan of the chest (+/- abdomen/pelvis depending on sites of known disease) but should also include all known sites of cancer (with exception of previously treated CNS lesions which do not need to be examined at each assessment). Scheduled on-treatment tumor assessments should begin 6 weeks after beginning nivolumab and continue thereafter every 6 weeks irrespective of dose interruptions or delays during the first 48 weeks of treatment, and every 12 weeks thereafter. Tumor assessments have a window of +/- 1 week from scheduled day. If an appropriate imaging study is done for an unrelated reason, it can be used for disease assessment.

 At screening, research bloods will be drawn for a) germline sequencing as a companion to somatic tumor DNA sequencing (1 blue top tube), b) T-cell subsets (4 CTP tubes)

 At C1D1, C2D1, C2D8, C3D1, C4D1, C5D1 and end-of-treatment, research bloods will be drawn for T-cell subsets (4 CTP tubes).

 The window for the on-treatment biopsy will be +/- 1 week from the date of C2D8. The corresponding research blood draw should be the same day of the on-treatment biopsy, +/- 1 day from the date of the biopsy [The +/- 1 day window should be applied to the date of the biopsy, not the date of C2D8].

All patients will be followed for survival and subsequent anti-cancer therapy approximately every 3 months until death, loss to follow-up, or study termination.

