## 11.0 TOXICITIES/SIDE EFFECTS

### 11.1 Nivolumab and Ipilimumab toxicity overview

Nivolumab and Ipilimumab are currently in clinical development and both have been FDA-approved for use as monotherapies respectively. The entire safety profile of nivolumab plus ipilimumab is not known at this time. Measures will be taken to ensure the safety of the patients participating in this trial, including the use of stringent inclusion and exclusion criteria and close monitoring. Toxicity grading will be performed in accordance with NCI CTCAE 4.0. If toxicities are encountered, adjustments will be made to the study treatment as detailed in the sections below. All AEs and SAEs will be recorded during the trial and for up to 100 days after the last dose of study treatment.

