#### 11.12 Serious Adverse Event

Reporting of SAEs is detailed in Section 17.2.

Clarification should be made between the terms *serious* and *severe* because they are not the same. The term *severe* is often used to describe the intensity (severity) of a specific event (as in mild, moderate, or severe myocardial infarction); the event itself, however, may be of relatively minor medical significance (such as a severe headache). This is not the same as *serious*, which is based on the patient/event outcome or an action criterion described above, and is usually associated with events that pose a threat to a patient's life or functioning. A severe AE does not necessarily need to be considered serious. For example, persistent nausea of several hours duration may be considered severe nausea but may not be considered an SAE. On the other hand, a stroke resulting in only a minor degree of disability may be considered mild but would be defined as an SAE based on the above noted criteria. Seriousness (not severity) serves as a guide for defining regulatory reporting obligations.

Following the patient's written consent to participate in the study, all SAEs, whether related or not related to study drug, must be collected, including those thought to be associated with protocol-specified procedures. All SAEs must be collected that occur during the screening period and within 100 days of discontinuation of dosing. If applicable, SAEs must be collected that relate to any later protocol-specified procedure (e.g., a follow-up skin biopsy). All SAEs should be followed to resolution or stabilization.

A **Serious** Adverse Event or Reaction is any AE occurring at any dose that:

- Results in death

- Is life-threatening (defined as an event in which the patient was at risk of death at the time of the event; it does not refer to an event that hypothetically might have caused death if it were more severe)
- Requires inpatient hospitalization or prolongation of existing hospitalization EXCEPT as noted below
- Results in persistent or significant disability/incapacity (defined as substantial disruption of a person's ability to conduct normal life's functions).
- Results in a congenital anomaly / birth defect
- Results in anaphylaxis related to study drug

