### **17.2.1 Procedures for Reporting Serious Adverse Events (SAEs) to Drug Sponsor**

Following the subject's written consent to participate in the study, all SAEs, whether related or not related to study drug, must be collected, including those thought to be associated with protocol-specified procedures. Adverse events (AEs) may be spontaneously reported by the patient and/or in response to an open question from study personnel or revealed by observation, physical examination, or other diagnostic procedures must be reported to BMS (or designee). AEs which are serious must be reported to BMS (or designee) from study enrollment up to and including 100 days after administration of the last dose of nivolumab. When possible, signs and symptoms indicating a common underlying pathology should be noted as one comprehensive event. Any SAE that occurs at any time after completion of nivolumab treatment or after the designated follow-up period that the investigator and/or sub-investigator consider to be related to any study drug must be reported to the BMS Worldwide Safety (or designee). The investigator should report any SAE that occurs after these time periods and that is believed to be related to study drug or protocol-specified procedure.

This is an investigator-initiated study. The principal investigator [name], who may also sometimes be referred to as the sponsor-investigator, is conducting the study and acting as the sponsor. Therefore, the legal/ethical obligations of the principal investigator include both those of a sponsor and those of an investigator.

For studies conducted under an Investigator IND, any event that is both serious and unexpected must be reported to the Food and Drug Administration (FDA) as soon as possible **and no later than 7 days**

(for a death or life-threatening event) **or 15 days** (for all other SAEs) **after the investigator's or institution's initial receipt of the information.** BMS will be provided with a simultaneous copy of all adverse events filed with the FDA.

SAEs should be reported on MedWatch Form 3500A or similar form. It **MUST** include the institutional **AND** BMS study ID [per study Agreement]

MedWatch SAE forms should be sent to the FDA at:

MEDWATCH  
[name]  
[name]  
Fax: [name] ([name])  
<http://www.accessdata.fda.gov/scripts/medwatch/>

All SAEs should simultaneously be faxed or e-mailed to BMS at:

Global Pharmacovigilance & Epidemiology  

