Bristol-Myers Squibb Company  
**SAE [contact]  
**SAE Email Address:** [[contact]](mailto:[contact])

The study period during which adverse events will be reported is from the initiation of study procedures to the end of the study treatment follow-up, defined as 100 days following the last administration of nivolumab treatment.

If only limited information is initially available, follow-up reports are required. (Note: Follow-up SAE reports should include the same investigator term(s) initially reported.) If an ongoing SAE changes in its intensity or relationship to study drug or if new information becomes available, a follow-up SAE report should be sent to BMS using the same procedure used for transmitting the initial SAE report.

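### Safety recording runs to day 100 after the last dose, but the Final visit may fall on day 86, and two sections differ on whether new therapy ends follow-up of an unresolved related SAE

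*Combined protocol and SAP*

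**What the plan says.** **Recording period.** Section 11.1 states: "All AEs and SAEs will be recorded during the trial and for up to 100 days after the last dose of study treatment". Section 9 (Follow-up Assessments after Last Dose of Study Treatment) and Section 11.12 use the same 100 days. Section 17.2.1 has SAEs reported to the drug manufacturer "up to and including 100 days after administration of the last dose of nivolumab", and its adverse event reporting period ends with a follow-up "defined as 100 days following the last administration of nivolumab treatment". It adds a duty that outlasts the window: "The investigator should report any SAE that occurs after these time periods and that is believed to be related to study drug".

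**Scheduled contact.** In the Section 10.0 calendar the Final visit is the only column after treatment. It carries adverse event assessment, history and physical, metabolic panel and blood count, and is timed at "100 days after last dose of study therapy (+/- 2 weeks". Contact about every 3 months continues afterwards, but for survival and subsequent therapy only.

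**Follow-up of ongoing events.** Section 9 covers treatment-related adverse events that are ongoing at study completion or discontinuation. They are followed until the first of several stops, which include "new anti-cancer treatment is initiated, the patient is lost to follow-up" and withdrawal of consent. It makes no exception for serious events. Section 11.12 says: "All SAEs should be followed to resolution or stabilization". Section 17.2.1 calls for a follow-up report "If an ongoing SAE changes in its intensity or relationship to study drug or if new information becomes available".

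**The concern.** The visit that closes safety follow-up can be held before the safety period ends. After an early visit, the calendar schedules no further questioning, examination or bloods for adverse events in the remaining days. Late related SAEs stay reportable without a time limit, so the exposure is mainly non-serious events and SAEs not judged related. Section 17 plans to tabulate adverse events by severity and causality, so these data are used.

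The second issue is two stop rules that give opposite instructions for the same event. The recorded outcome of an unresolved related SAE could then depend on which section the staff follow. Section 11.1 says the full safety profile of the combination is not yet known, which is why complete capture matters here.

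**Working it through.** The plan states no figure to reproduce. The first part is date arithmetic and the second is a comparison of text.

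**Part 1: visit window**

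Inputs: target day 100 and tolerance 14 days (Section 10.0); recording to day 100 (Sections 9, 11.1, 11.12 and 17.2.1).

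- Earliest compliant visit: 100 − 14 = day 86.
- Latest compliant visit: 100 + 14 = day 114.
- Permitted visit days: 114 − 86 + 1 = 29.
- Permitted days before day 100 (86 to 99): 14, and 14/29 = 48%. On or after day 100 (100 to 114): 15, and 15/29 = 52%.
- Recording days left after a day-86 visit (87 to 100): 100 − 86 = 14, and 14/100 = 14% of the recording period.
- With a window of day 100 to day 114: 114 − 100 + 1 = 15 permitted days, and 100 − 100 = 0 recording days left after the earliest visit.

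**Part 2: a related SAE, ongoing when the patient leaves the study, neither resolved nor stable, and new therapy starts**

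| Provision | Applies to | Does new therapy end follow-up? |
|---|---|---|
| Section 9, Follow-up Assessments after Last Dose | Treatment-related events, serious or not, ongoing at completion or discontinuation | Yes |
| Section 11.12 | All SAEs, related or not | No; only resolution or stabilization |
| Section 17.2.1 | Ongoing SAEs that change | Not addressed; a follow-up report is required |

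Once the event has resolved or is stable, Sections 9 and 11.12 agree. They differ only in the case above, and no text says which governs.

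**The case against.** **A visit tolerance is not a recording rule.** This stands in part. The duty to record runs to day 100 whatever the visit date, and Section 17.2.1 accepts spontaneously reported events. A reader might infer that recording stops at an early Final visit, or that 14% of late safety data will be lost. The documents support neither. The 14 days are a worst-case scheduling tolerance, and the 48% merely counts permitted days. Without a distribution of visit dates it says nothing about how often visits fall early.

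**Other contacts may cover these days.** Section 9 (Toxicity monitoring and adverse events) requires toxicity assessment at least every 2 weeks while the patient remains on study. Section 13.0 speaks of leaving the treatment phase, which suggests that a patient can be off treatment yet still on study. But the term is not defined, and the calendar shows no such visits after the last dose. Section 9 also continues tumor scans for patients who stopped without progression, so some will be seen after an early Final visit. Those are not adverse event assessments, and they do not extend to patients who stopped for progression. The point is therefore confined to what the calendar schedules.

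**The specific rule governs the general one.** Reading Section 11.12 as the rule for SAEs is sensible and would settle the matter, and Section 17.2.1 points the same way. A reader might infer that the protocol directs staff to abandon unresolved SAEs, which goes too far. What remains is that the Section 9 rule has no exception for SAEs and nothing states the order of precedence.

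**Conclusion.** Both parts hold, and both are minor.

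1. Up to 14 days of the 100-day recording period can pass with no adverse event assessment in the calendar.
2. The stop rules in Sections 9 and 11.12 differ for a narrow class of related SAEs. The documents do not say how many patients would be in that position, so no number is estimated.

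The arithmetic takes two weeks as 14 days and treats the last nivolumab dose as the last dose of study therapy, because the sections count day 100 from one or the other. The first part also rests on the calendar being the schedule that staff follow. The effect is on completeness of safety capture. A reader might extend it to the response or biomarker results, but those rest on tumor assessments and specimens, which neither provision changes.

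**What to change.** **Section 10.0.** Set the Final visit to day 100 after the last dose, with a window of 0 to +14 days. No visit is added. The cost is a window of 15 days instead of 29, and slightly more patients may have begun new therapy by the time they are seen.

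**Section 9, Follow-up Assessments after Last Dose of Study Treatment.** Exempt SAEs from the new-therapy stop and state that they are followed under Section 11.12. Keep loss to follow-up (already in Section 9) and withdrawal of consent (Sections 9 and 13.0) as reasons to stop. The cost is that some late SAE follow-up will be confounded by the new therapy. Its start date is already needed in Section 12, for best overall response and for PFS censoring, so it can be used for attribution without new data collection.
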